11.2.1 List of Laboratory Parameters

The following table presents a list of all laboratory parameters tested. The column "Summarize" indicates which laboratory tests will be summarized as described in section 11.2, above. Results for all other tests will be listed only.

Lab category	Lab test	Summarize
CHEMISTRY	ALT (SGPT)	Y

23 of 31

Lab category	Lab test	Summarize
	APTT-FSL-QT	
	AST (SGOT)	Y
	Albumin-BCG	
	Aldolase-335	
	Alkaline Phosphatase-QT	Y
	Calcium (EDTA)	
	Cholesterol (High Performance)	
	Creatine Kinase	
	Creatinine (Rate Blanked)	Y
	D-Dimer	Y
	Direct Bilirubin	Y
	Direct HDL-C 3rd Generation-QT	
	Folate	
	GFR by MDRD-QT	Y
	Haptoglobin-QT	Y
	Indirect Bilirubin	Y
	International Normalized Ratio	
	LDH	Y
	LDL Chol-Friedewald 3rd -QT	
	Magnesium	
	Phosphorus	
	Prothrombin Time	
	Rheumatoid Factor-CL-QT	
	SPE M-spike Qty 1	
	SPE M-spike Qty 2	
	SPE Total M-Protein	
	SPE-M-spike 1(%)-CL	
	SPE-M-spike 2(%)-CL	
	Ser Electrophoresis-Albumin(%)	
	Serum Bicarbonate	
	Serum Chloride	
	Serum Glucose	
	Serum Potassium	
	Serum Sodium	
	Total Bilirubin	Y
	Total Protein	-
	Triglycerides (GPO)	
	Urea Nitrogen	
HEMATOLOGY	-	
III.WII II OLOGI	Basophils, Basophils (%)	Y

24 of 31

Effective Date 28-Aug-2023

Effective

Status

Version 3.0

Lab category	Lab test	Summarize
	Eosinophils, Eosinophils (%)	Y
	Lymphocytes, Lymphocytes (%)	Y
	Monocytes, Monocytes (%)	Y
	Neutrophils, Neutrophils (%)	Y
	Platelets	Y
	Reticulocyte Count %-CL	Y
	WBC	Y
	Anti-Thyroglobulin	
	Free T3	
	Free Thyroxine	
	IFN Gamma	Y
	IL-1	Y
	IL-4	Y
	IL-6	Y
	IL-10	Y
	IL-13	Y
	Immunoglobulin IgA-QT	
	Immunoglobulin IgGQT	
	Immunoglobulin IgMQT	
	Ser Electrophoresis-Albumin	
	Ser Electrophoresis-Alpha 1	
	Ser Electrophoresis-Alpha 2	
	Ser Electrophoresis-Alpha1 (%)	
	Ser Electrophoresis-Alpha2 (%)	
	Ser Electrophoresis-Gamma	
	Ser Electrophoresis-Gamma (%)	
	TNFalpha (-70)-TAT60d-RUO-CL	Y
	TSH 3rd Generation-QT	
	TSH 3rd IS	
	Thyroperoxidase Antibody	
	Total Thyroxine	
	Vitamin B12	
URINALYSIS	Ur Blood	
	Ur Glucose	
	Ur Hyaline Casts/LPF	
	Ur Ketones	
	Ur Leukocyte Esterase	
	Ur Nitrite	
	Ur Protein	
	Ur RBC/HPF	Y

Lab category	Lab test	Summarize
	Ur Renal Tubular Epi Cells	
	Ur Specific Gravity	Y
	Ur Squamous Epithelial Cells	
	Ur Transitional Epi Cells	
	Ur Urobilinogen	
	Ur WBC/HPF	Y
	Ur pH	Y

All parameters indicated as "Y" will be summarized, all other parameters will be listed only.

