4.5.2.6 Hemolysis detection

During all the infusion visits, hemolysis detection will be evaluated using: (1) blood assessments including whole blood hemoglobin, serum or plasma free hemoglobin, haptoglobin, lactate dehydrogenase (LDH), direct antiglobulin test (DAT), absolute reticulocyte count (ARC), red blood count (RBC), hematocrit, total and indirect bilirubin, and blood smear within 8 hours prior to the infusion; (2) urinalysis including urinary sediment and hemoglobinuria within 8 hours prior to the infusion; and (3) clinical parameters including red/dark urine, jaundice, as well as other signs and symptoms of anemia (such as pallor or tachycardia) evaluated at any time on the day of infusion before the infusion (Day 1), at any time on the day of infusion after the completion of the infusion (Day 2), and 10 days (±2 days) after the initiation of the infusion (Day 1) by a phone call.

After getting results from (1) to (3) and prior to the next study visit, a medical doctor will assess the hemolysis considering algorithm provided in ANNEX 14 from IV1 (Week 0) to IV13 (Week 48).

Sites affected by the COVID-19 pandemic can refer to ANNEX 18 for extraordinary contingency measures to be implemented.

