4.2 Safety Variables

The following safety variables will be assessed:

- Adverse Events (AEs), adverse reactions (ARs), suspected adverse drug reactions (ADRs), serious AEs (SAEs), AEs leading to the discontinuation of the study, AE with special interest (AESI), and infusional AEs. Section 11.1 provides definitions of AE endpoints.
- Blood biochemistry (creatinine, blood urea nitrogen (BUN), alanine aminotransferase (ALT), aspartate aminotransferase (AST), alkaline phosphatase (AP) and total bilirubin (TB)) and cell counts (complete blood count (CBC), including differential leukocyte count)
- Vital signs (heart rate, blood pressure, respiratory rate, and temperature)
- Physical assessments

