5 GENERAL STATISTICAL CONSIDERATIONS

Statistical analyses and data presentations will be generated using SAS version 9.2 or higher.

Unless otherwise noted, for continuous variables, descriptive statistics will include the number of non-missing values, mean, standard deviation, median, minimum and maximum. The minimum and maximum will be presented to the same number of decimal places to which the data were recorded, the mean and median will be presented to 1 decimal place more than the data were recorded and the standard deviation will be presented to 2 decimal places more than the data were recorded.

For categorical variables, descriptive statistics will include counts and percentages per category. Percentages will be presented to 1 decimal place. Percentages of 0 and 100 will be reported as whole numbers (i.e. "0%" and "100%", respectively).

Unless otherwise noted, all statistical inference will be tested at 2-sided with α =0.05. P-values will be presented to 4 decimal places and confidence intervals will be presented to the same number of decimal places as the corresponding point estimate.

Unless otherwise noted, all data collected in the electronic case report forms (eCRFs) or electronically transferred (such as central laboratory data) will be presented in data listings. Subjects will be identified in the data listings by subject number (which includes site number)

and grouped by treatment arm. All summaries and listings will be presented by treatment arm and by study stage (i.e., Stage 1, Stage 2, and Overall) if appropriate.

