11.2 Laboratory Assessments

Blood biochemistry and cell counts data will be collected at the assigned visits according to the protocol and will be stored and/or testing performed by a central laboratory.

The lab parameters will be summarized using number of subjects, mean, standard deviation, median, minimum, and maximum values at each visit for continuous variables, and counts and percentages for categorical variables. Change from baseline to each scheduled post-baseline visit will be summarized for each continuous variable. Shift tables, based on the high/low flags, will also be summarized for each parameter at each visit.

All laboratory data will be presented in data listings.

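### SAP 11.2.1, as read from the PDF, has no row for haemoglobin, haematocrit or red cell count, so the red-cell part of a named safety variable would be listed but not summarised by arm

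*SAP*

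**What the plan says.** SAP 4.2 includes "cell counts (complete blood count (CBC), including differential leukocyte count" among the safety variables. SAP 11.2 plans descriptive statistics by visit and change from baseline, and adds: "Shift tables, based on the high/low flags, will also be summarized for each parameter at each visit". It also states: "All laboratory data will be presented in data listings". Section 5 sets the layout: "All summaries and listings will be presented by treatment arm and by study stage" where appropriate.

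SAP 11.2.1 decides which tests receive this treatment. The section opens with "The following table presents a list of all laboratory parameters tested" and explains that a column headed Summarize marks the tests to be handled as in 11.2. Its closing line says that parameters marked Y "will be summarized, all other parameters will be listed only".

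Protocol 4.5.2.6 requires a haemolysis blood panel at every infusion visit. It begins with "whole blood hemoglobin, serum or plasma free hemoglobin, haptoglobin, lactate dehydrogenase (LDH), direct antiglobulin test (DAT), absolute reticulocyte count (ARC), red blood count (RBC" and continues with haematocrit, total and indirect bilirubin, and a blood smear.

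**The concern.** The SAP presents the table as complete and makes it the only route to a summary, so a test without a row is listed and nothing more. The haematology block as read contains the white-cell differential, platelets, reticulocyte percentage and total white cells. The red-cell half of the complete blood count is missing, and no reason is given.

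This matters because protocol 9.3.7.2 makes haemolysis an event of special interest, and protocol 6.3 makes a confirmed, clinically significant case a ground for ending participation. Protocol 2.3 cites haemolytic reactions with intravenous immunoglobulin. Stage 1 compares two doses with placebo, and the safety objective in SAP 3.2.3 is a comparison with placebo. Under protocol 9.2.4 an abnormal laboratory value becomes an adverse event only if the investigator judges it clinically relevant. A small average fall in haemoglobin, spread over many patients in one arm, would therefore not reach the adverse event tables. A change-from-baseline table by arm is where it would be seen.

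**Working it through.** The point involves no power, alpha or sample-size figure. The check sets the protocol panel beside the SAP table.

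**Step 1: match the panel item by item.** Inputs: the blood items in protocol 4.5.2.6 and the rows and Y flags in SAP 11.2.1.

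| Protocol haemolysis blood item | Row in SAP 11.2.1 | Treatment |
|---|---|---|
| Whole blood haemoglobin | none | listed only |
| Free haemoglobin | none | listed only |
| Haptoglobin | yes, Y | summarised |
| LDH | yes, Y | summarised |
| Direct antiglobulin test | none | listed only |
| Absolute reticulocyte count | percentage only, Y | summarised as % |
| Red cell count | none | listed only |
| Haematocrit | none | listed only |
| Total bilirubin | yes, Y | summarised |
| Indirect bilirubin | yes, Y | summarised |
| Blood smear | none | listed only |

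Result: 6 items without a row + 5 with a Y row = 11. This counts reticulocyte percentage as a match for the absolute count. On a strict reading, 7 of 11 have no row.

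**Step 2: compare with SAP 4.2.** The complete blood count is a safety variable. Its white-cell, differential and platelet components all carry Y. Haemoglobin, haematocrit and red cell count do not appear, so the table contradicts section 4.2 for these three.

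**Step 3: ask whether they were dropped on purpose.** SAP section 12, on changes to protocol-specified analyses, records only the cytokine change. IL-17 and IL-23 also have no row in 11.2.1, and there section 12.1 explains that available results will only be listed. No such statement exists for the red-cell measures.

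**Step 4: ask whether the rows were lost when the PDF was read.** Within a category the rows run essentially alphabetically. Haematocrit and haemoglobin would fall between eosinophils and lymphocytes, and red cell count between platelets and reticulocytes. Both pairs are adjacent in the text, in the middle of a page. The visible damage is elsewhere: a garbled row at the head of the block, before basophils, and a page break between basophils and eosinophils. An antiglobulin row could have stood at that break. Loss of the three red-cell rows is unlikely but cannot be excluded without the PDF.

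**Step 5: how often the measures are scheduled.** Protocol 4.5.2.7 places the complete blood count at 8 visits: screening and Weeks 0, 12, 24, 36, 52, 64 and 76. The haemolysis panel is taken at 13 infusion visits. Four of these (Weeks 0, 12, 24, 36) overlap, so if the count includes the three red-cell measures, they are scheduled at 8 + 13 − 4 = 17 visits.

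**The case against.** The strongest objection is that the omission may be an artefact. When a program drops a row, the remaining rows close up, so an intact alphabetical run is weak evidence. The table shows other signs of damage or loose compilation. The block from anti-thyroglobulin to vitamin B12 has no category label, and the electrophoresis rows pass from alpha-2 to gamma with no beta row and no visible gap. This stands as a reason to check the source before acting. It does not make loss likely at two separate, undamaged places.

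A second objection is that the list is simply incomplete. ESR, haemoglobin A1C, antinuclear antibodies and the HCV and HIV antibodies have no row either. That is fair, and it suggests oversight. A reader might infer a decision to leave haemoglobin untabulated, but the documents contain no such decision. A clerical omission under a stated rule still yields no table.

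Third, one could read the sentence on shift tables in 11.2 as covering every parameter whatever its flag. Section 11.2.1 says, however, that the Y column determines which tests are handled as 11.2 describes, so shift tables follow the flag.

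Fourth, protocol 10.1.3 says in general that laboratory tests are both listed and tabulated, but its specific paragraph on biochemistry and cell counts commits only to listing. Protocol 9.1 limits laboratory safety endpoints to biochemistry and cell counts, which 4.5.2.7 defines without free haemoglobin or the antiglobulin test. This also stands. A claim that the SAP breaches the protocol is weak, and tables for those extra tests are optional. The conflict between SAP 4.2 and 11.2.1 is unaffected.

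**Conclusion.** The point holds in a limited form. As the text reads, three components of a named safety variable have no row in the table that controls summaries, and 6 of 11 protocol haemolysis blood items would be listed only. A sub-clinical, dose-related fall in haemoglobin would appear in no by-arm table.

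A reader might infer that haemolysis goes unreported by arm, or that its main measures are left out. The documents do not support this. Haptoglobin, LDH, total and indirect bilirubin and reticulocyte percentage are all summarised. SAP 11.1 tabulates events of special interest by treatment group, and protocol 10.1.3 calls for a separate summary of haemolytic events. A medical doctor assesses haemolysis after each infusion visit under protocol 4.5.2.6. Neither document ranks one marker above the others. No data are lost, because every laboratory result is listed.

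Nor should the gap be sized by the planned enrolment. SAP section 2 records that the trial was stopped early, and the number randomised is not given.

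The conclusion assumes that the rows are absent from the source PDF and that 11.2.1 is applied as written. It concerns safety reporting and does not touch the primary analysis.

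**What to change.** First check SAP 11.2.1 in the source file. If the rows are absent, add haemoglobin, haematocrit and red cell count with Y, so that they receive by-visit statistics, change from baseline and shift tables by arm. This brings the table into line with SAP 4.2.

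Optionally, add free haemoglobin and the absolute reticulocyte count with Y, and the direct antiglobulin test as a categorical parameter. All come from samples the protocol already schedules.

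During the same check, look at urea nitrogen. It has a row without Y although SAP 4.2 names it as a safety variable; the row lies next to the damaged heading, so the flag may have been lost in reading. If other tests are deliberately left out of the table, its opening line should not describe the list as complete.

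The cost is a few table rows and outputs. No new procedure, sample or patient visit is needed.

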4.5.2.7 Blood biochemistry and cell counts

Laboratory test will include:

- Renal parameters: creatinine, blood urea nitrogen (BUN) and GFR.
- Hepatic parameters: alanine aminotransferase (ALT), aspartate aminotransferase (AST), alkaline phosphatase (ALP), and total bilirubin (TBL).
- Haematological parameters: complete blood count (CBC), including differential leukocyte count.

Samples for blood biochemistry and cell counts testing will be collected at the SV (Week -4 to -1), within 8 hours prior to investigational product infusion at the IV1 (Week 0), IV4 (Week 12), IV7 (Week 24), IV10 (Week 36), and at EoTV (Week 52), FU3 (Week 64), and FV (Week 76).

Blood samples will be sent to a central laboratory for measurement of blood chemistry and cell count. Laboratory results must be reviewed by a medical doctor.

Sites affected by the COVID-19 pandemic can refer to ANNEX 18 for extraordinary contingency measures to be implemented.

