- 12. Rest period (sitting on a chair for at least 30 minutes and until the subject feels fully recovered after completion of the MMT).
- 13. Muscle strength: Baseline QMT.

14. Randomization.

Individuals who fulfill all inclusion criteria and none of the exclusion criteria and have undergone all screening and enrollment assessments will be considered eligible to continue in the clinical trial. These subjects will be randomized to 1 of the treatment arms and will be included in the *IWRS Randomization*. Randomization is to be stratified based on the body part (lower extremities versus upper extremities) that was most significantly affected by PPS at the SV.

Individuals who do not fulfill all of the inclusion criteria, fulfill any of the exclusion criteria, or have not undergone all enrollment assessments will be considered enrollment failures. If a subject is ineligible for the clinical trial, their demographic data and specific reason for ineligibility will be captured on the appropriate eCRF page and on the medical history eCRF.

INFUSION VISIT 1:

Investigational product will be infused at IV1 over 2 consecutive days (Day 1 and Day 2) which will start on the same day or after finishing the Enrollment Visit.

Infusion Day 1:

- 1. Blood testing (blood sample collected within 8 hours prior to the infusion):
 - Blood biochemistry and cell counts: CBC, including differential leukocyte count, creatinine, BUN, ALT, AST, ALP, TBL, and GFR.
 - D-dimer blood level for thromboembolic events risk assessment.
 - Hemolysis detection: whole blood hemoglobin, serum or plasma free hemoglobin, haptoglobin, LDH, DAT, ARC, RBC, hematocrit, total and indirect bilirubin, and blood smear.
 - Inflammatory cytokines: IL-1, IL-4, IL-6, IL-10, IL-13, IL-17, IL-23, TNF-alpha, and IFN-gamma.
 - Retention blood sample for possible viral exposure testing (sample will be tested only if subject shows signs and symptoms of viral infection during the study).
 - Retention blood sample for possible future biomarker testing.
- 2. Urine testing (urine sample collected within 8 hours prior to the infusion):
 - Urine sediment and measuring of hemoglobinuria.
- 3. Infusion and vital signs:
 - Infusion of investigational product.
 - Subject vital signs (T, RR, HR, SBP and DBP) will be monitored: (1) within 20 minutes before the beginning of each infusion; (2) every 30 ± 10 minutes during the first hour of each infusion; and (3) at 30 ± 10 minutes post-completion of each infusion.

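### SAP 11.2.1 leaves BUN, a named safety variable, and urine blood as listing-only, so neither gets a by-arm summary; a small inconsistency within the SAP

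*SAP*

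**What the plan says.** SAP 4.2 sets out the safety variables. The biochemistry list opens "Blood biochemistry (creatinine, blood urea nitrogen (BUN), alanine aminotransferase (ALT" and goes on to AST, alkaline phosphatase and total bilirubin, six variables in all. Protocol 4.5.2.7 groups BUN with the kidney tests: "Renal parameters: creatinine, blood urea nitrogen (BUN) and GFR".

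SAP 11 states as a general rule that the combined safety data are summarised by treatment arm. SAP 11.2 says what a summarised laboratory test receives: descriptive statistics or counts at each visit, change from baseline for continuous tests, and shift tables based on high/low flags.

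SAP 11.2.1 then decides which tests get this. Its introduction says of tests without a flag: "Results for all other tests will be listed only". The note under the table repeats the rule: "All parameters indicated as 'Y' will be summarized, all other parameters will be listed only". The row "Urea Nitrogen" and the urine blood row both have an empty flag cell.

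For haemolysis, protocol 4.5.2.6 requires "urinalysis including urinary sediment and hemoglobinuria within 8 hours prior to the infusion" at every infusion visit. The visit schedule in protocol 5.2 carries this through, for example at Infusion Visit 1: "Urine sediment and measuring of hemoglobinuria".

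**The concern.** SAP 4.2 and SAP 11 lead the reader to expect a by-arm summary of BUN. SAP 11.2.1 removes it without giving a reason, and BUN is the only one of the six named biochemistry variables treated this way. The urine blood row raises a similar question: urine pH and specific gravity are tabulated, while the row closest to the protocol's haemoglobinuria test is not.

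Both bear on risks that the trial recognises. Protocol 2.3 names rises in creatinine, acute renal failure and haemolytic reactions among the effects seen with immunoglobulin, and protocol 9.3.7.2 makes haemolysis an event of special interest. A listing shows individual values but gives no group mean, change or shift. A moderate shift in BUN in one arm, or a higher frequency of positive urine results, could therefore go unseen if no single value was judged clinically relevant.

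**Working it through.** No sample size, power or error rate is involved. The check sets the flag column of SAP 11.2.1 against the measures named elsewhere.

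**Biochemistry variables named in SAP 4.2**

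| Variable | Flag in SAP 11.2.1 |
|---|---|
| Creatinine | Y |
| BUN (urea nitrogen) | blank |
| ALT | Y |
| AST | Y |
| Alkaline phosphatase | Y |
| Total bilirubin | Y |

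Five of six are flagged; BUN is the exception.

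**Renal parameters in protocol 4.5.2.7.** Creatinine and GFR are flagged and BUN is blank, so two of three are summarised.

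**Urinalysis rows.** The table shows 15. Four are flagged: red cells per high-power field, specific gravity, white cells per high-power field, and pH. Eleven are blank, urine blood among them. The protocol names two urine components for haemolysis:

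- Sediment: the red cell count is flagged, so this is at least partly covered.
- Haemoglobinuria: no row has this name. Urine blood is the only row that appears able to hold the result.

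**Other markers relevant to haemolysis.** Haptoglobin, LDH, total and indirect bilirubin, and reticulocytes are all flagged.

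**Reliability of the two blank cells.** The available text of the table is damaged in places. The urea nitrogen row stands directly above a broken haematology heading, and there is a stray mark in the total protein row a little higher up. A lost flag for BUN therefore cannot be excluded. The urine blood row is the first row of the urinalysis block, and the text around it is clean.

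**After the change.** The biochemistry count goes from 5 of 6 to 6 of 6, the renal count from 2 of 3 to 3 of 3, and the urinalysis count from 4 of 15 to 5 of 15.

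**The case against.** The strongest case against has four parts.

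1. *Urine blood is not a named safety variable.* This stands. SAP 4.2 lists no urinalysis, and the protocol speaks of haemoglobinuria and sediment, not urine blood. The link is an inference, so BUN is the stronger half of the point.

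2. *The protocol does not promise more.* This largely stands. Protocol 9.2.4, and the paragraph on biochemistry and cell counts in 10.1.3, commit only to listing these data. The opening of 10.1.3 mentions tabulation alongside listing for safety data in general, but assigns it to no particular laboratory test. A reader might infer a breach of the protocol; the text does not support that. The conflict lies within the SAP. One can add that SAP 11.2.1 is the more specific rule and so governs, but that tells the programmer what to do without explaining why one named variable is treated differently.

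3. *The arms can still be compared.* A reader might take listing-only to mean that these results are never seen by arm. That goes too far. SAP 5 groups listings by treatment arm. Under protocol 10.1.3, out-of-range blood results that the investigator judges clinically relevant become adverse events, and SAP 11.1 tabulates adverse events, including those of special interest, by treatment group. What is missing is a group summary of the values themselves. The adverse event route depends on the investigator's judgement and does not replace it.

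4. *A urine table would add little.* The scheduled urine sample is taken before the infusion, so it says little about haemolysis in the hours after dosing. This is fair and limits the gain, but it applies equally to the urine tests that are flagged.

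**Conclusion.** The point holds as a minor inconsistency within the SAP. BUN is a named safety variable, is the only one of six biochemistry variables left without a flag, and is listing-only under a rule stated twice. The urine blood row has the same status and appears to be the only place for the haemoglobinuria result. The effect is modest: renal function is still summarised through creatinine and GFR, and haemolysis through haptoglobin, LDH, bilirubin, reticulocytes and urine red cells. No efficacy estimate or error rate changes.

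The conclusion rests on two assumptions: that the blank BUN cell is blank in the source PDF, and that urine blood is where haemoglobinuria is recorded.

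A reader might also notice that haemoglobin, haematocrit and red cell count do not appear in the table, and infer that the SAP omits them. The documents do not support that inference. Several other tests required by the protocol are absent from the same text, among them haemoglobin A1C, ESR and the direct antiglobulin test, and the table is visibly damaged. The gap may come from the text conversion and should not be counted against the plan.

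**What to change.** First check the urea nitrogen cell in the source PDF. If it is blank, mark urea nitrogen as Y in SAP 11.2.1. Mark urine blood as Y as well or, if haemoglobinuria is recorded under another name, name that result in the table and mark it Y. If either test is meant to remain listing-only, give the reason in SAP 11.2.1 and bring SAP 4.2 and SAP 11 into line.

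BUN would then receive by-visit statistics, change from baseline and shift tables by arm. The urine result would receive the same if it is numeric, or counts and percentages if it is categorical, with shift tables where high/low flags exist.

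The cost is a few extra descriptive tables. Under protocol 4.5.2.7, BUN is scheduled at six visits after baseline (Weeks 12, 24, 36, 52, 64 and 76), and under protocol 5.2 urine is collected at each of the 13 infusion visits. No new data collection is needed, and sample size, power and alpha do not change.
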